Study Design

This project will have several components, which we anticipate will unfold over the course of 5 years. The first step of the process will be training research and clinical staff; practicum students, psychology residents, and staff clinicians at CAMH on administering the Modular Approach to Therapy for Children with Anxiety, Depression, Trauma, and Conduct Problems (MATCH-ADTC) treatment. The study investigators will be primarily involved in training clinical staff on MATCH-ADTC treatment. They will not be directly involved in administering care, but they will be responsible for supervising practicum students and residents administering care. These students are clinical trainees in a doctoral program for clinical psychology, supervised by registered psychologists at CAMH (e.g., [name], [name]). These students have previously completed coursework and training in therapeutic methods. When matching clients to students, we will consider the expected length of treatment in relation to the length of their practicum or residency. Most practicums and residencies range from 9 months to 12 months, which will provide ample time to complete most courses of treatment. In the case that a student is unable to complete a course of treatment for a client, we will ensure continuity of care as is standard within our clinical services. There would be a plan for a warm transfer, where another trainee or clinician would continue treatment.

Children and their parent(s)/caregiver(s) will be recruited on an ongoing basis from two outpatient children's mental health clinics (CAMH and University of Guelph). Senior research staff will screen families, enroll them in the study, and conduct pre-treatment assessments. After enrolment and collection of initial measures, participants will be randomly assigned to the intervention arm or the waitlist control arm. We anticipate that the duration of both MATCH-ADTC treatment and the waitlist will range between 4 – 6 months, which is similar to the usual wait times for services at both clinics.

During this period, participants in both arms will complete brief weekly measures, which consist of very brief symptom scales. Participants will be required to complete quarterly assessments (approximately 3 months following their initial assessment), which will consist of symptom scales, medication tracking, clinical interviews, experimental tasks and physiological measures.

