Following the intervention or waitlist period, our team will conduct post- assessments. The post-assessments will allow us to analyze any changes in biobehavioural regulation and compare the differences between the intervention and control arms. Participants in the control arm will complete the post assessment approximately 4-6 months after their initial assessment, or prior to them being picked up off the waitlist for treatment in the clinic. . As screening and enrolment are ongoing, we will consistently clean data and engage in quality assurance procedures to ensure our methods are rigorous and meet scientific standards.

Participant Recruitment

Children will be recruited from the Child, Youth, and Emerging Adult Program (CYEAP) at CAMH and at the Maplewoods Centre for Family Therapy and Child Psychology at the University of Guelph.

Approximately 250 families (children aged 8 – 15, and their parent(s)/caregiver(s)), seeking psychotherapy for child anxiety, depression or disruptive behaviour will be recruited for this study. Families recruited from CAMH will have been referred to the Better Behaviours Service or Mood & Anxiety Clinic, or will be on the psychiatric assessment waitlist. Many families on the waitlist wait over a year for psychiatric evaluation, and many do not need or benefit from an assessment because they have been referred specifically for psychosocial treatment, and may already have a diagnosis and prescribed medication. To reduce the wait times for families and reduce the assessment burden, clinicians will screen families before their psychiatric assessment to identify children who may benefit from directly receiving psychosocial treatment without needing a psychiatric assessment first. These families will be contacted and asked to complete a short clinical screening (i.e. reason for referral) and approached to participate in research if the clinical team thinks the family would be a good fit. This process follows a similar procedure previously approved for use in our clinic (REB #018/2022).

Initial Research Contact

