If the clinical-research team member is the first point of contact discussing research in detail, clients are given the opportunity to participate in a clinical trial, learn about the potential benefits of treatment, as well as the risks and alternatives. This process follows a core GCP principle of *respect for persons and beneficence* in that all clients are given the opportunity to choose if they want to participate in a clinical trial or not after receiving detailed information about the potential risks, benefits, and alternatives to participation. Efforts are taken to provide all possible options and alternatives to reduce any perceived or actual pressure on clients. Additionally, our consent form is structured in a way that participants can decline aspects of the study and still participate in others and receive treatment. If families choose not to participate in research, they are provided with the standard of care at the BBS and MAC, which includes assessment and treatment services as usual.

Sample Size

A Monte-Carlo simulation study with 1000 replications, moderate treatment effect ($d = 0.5$) α of 0.05 and β of 0.2, and 25% as the proportion mediated resulted in a required sample size of $N = 168$. We anticipate an attrition rate for both the intervention arm and the waitlist arm to be 20%, so we increased our sample size to 202. The Child, Youth and Family Services at CAMH and Maplewoods Centre at Guelph receive approximately 400 new child referrals per year within the age range and diagnostic criteria, so this target is quite feasible.

Clinical Records

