Videos will be recorded using an ipadaudio will be recorded via a digital recorder for the purpose of transcription, qualitative coding and fidelity checks. Recordings will be transferred via secure file transfer to the research team at the University of Guelph for transcription and coding. Once transferred, the video and audio recordings on the devices will be deleted from the recording devices and will be stored on encrypted hard drives at CAMH and secure servers at Guelph. The folder containing all video/audio recordings will be accessible only to members of the research team who have received appropriate training. Video and audio recording files will be retained at both sites for 10 years.

Once a participant agrees to participate in this study and signs the consent form, a research note will be generated on their medical record.

Participant Randomization

Stratified randomization by gender (boy, girl and non-binary) and age group (ages 8 – 10, 11 – 13, 14 – 15) will be employed to ensure balance in sample size between treatment and control groups with regard to gender and age randomization. REDCap will be employed and will allocate the participants based on a computer-generated randomization list using random block sizes. Allocation concealment will be achieved since the person making this assignment will have no awareness or control over the randomization schedule.

Data Collection

Measurement for this study will be multi-modal and will consist of questionnaires for the parent(s)/caregiver(s) and child, behavioural/cognitive tasks, a parent-child interaction task, and physiological measures. Data collection will be conducted by trained research staff with the supervision of the study investigators. The study investigators will conduct regular meetings with the

Parent and child questionnaires will be administered electronically via REDCap. In order to ensure consistency between the two sites (CAMH and Guelph), we will use a shared REDCap Project to administer questionnaires to participants. REDCap questionnaires, behavioural/cognitive tasks, parent-child interaction task, and physiological measures will be completed at each study visit. Additionally, parents and children will complete brief weekly questionnaires via secure, encrypted links from REDCap.

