Preliminary analyses will test for significant differences in demographic factors between the MATCH and waitlist groups; significant factors will be covaried in our models. In the unlikely event that medication discrepancies are discovered between the two treatment groups, we will equate the groups by imposing propensity scores-based weighting in the analysis. An exploratory factor analysis (EFA) will examine whether the emotion regulation variables load onto a broad latent construct. Variables that do not load on the same factor will be examined independently within our mediation models. Latent Growth Curve (LGC) mediation modeling, which will account for the nested structure of the data as well as potentially unequally spaced time points, will test whether improvements in emotion regulation mediate improvements in symptoms as a result of MATCH treatment. We will conduct two types of mediation analyses corresponding to our operationalization of treatment response – pre-post change and trajectory of change. First, emotion regulation (latent biobehavioural regulation factor(s) from the EFA) will be modeled as a latent change from baseline to the 3-month quarterly assessment, and symptom change (CBCL/YSR internalizing and externalizing scores) will be modeled as a latent change from baseline to the post assessment. Our predictor will be specified as MATCH vs. Waitlist to ensure we can derive conclusions about the impact of MATCH on emotion regulation and symptoms. To test the mediated effect, we will apply the recommended bootstrap-based product of coefficients, which will yield bias-corrected 95% CIs based on the recommended asymmetric CI method. Second, to understand trajectories of change during MATCH treatment, we will apply LGC modeling to examine latent slopes of change in emotion regulation (weekly CADS) and symptoms (weekly BFS) and explore the temporal relations between the two trajectories. This will allow us to understand the temporal order and bi-directionality of changes in regulation and symptoms. In both modeling approaches, we will co-vary child age, gender/sex, medication use, puberty status, ethnicity, and treatment fidelity. We will apply an intent-to-treat approach and full information maximum likelihood estimation to account for potential bias caused by missing data.

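### Site is left out of both the stratification and the covariate list of a two-clinic mediation trial, so it can confound the mediator-outcome path

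*Protocol*

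**What the plan says.** - **Recruitment.** The protocol's Study Design section says families come from two outpatient children's "mental health clinics (CAMH and University of Guelph"). Participant Recruitment describes the CAMH streams: "Families recruited from CAMH will have been referred to the Better Behaviours Service or Mood & Anxiety Clinic", or will be waiting there for a psychiatric assessment. The route into the Guelph clinic is not described.
- **Randomisation.** Participant Randomization specifies "Stratified randomization by gender (boy, girl and non-binary) and age group". Site is not a stratum.
- **Covariates.** Data Analysis fixes one list for both modelling approaches: "we will co-vary child age, gender/sex, medication use, puberty status, ethnicity, and treatment fidelity". Site is not on it.
- **Data-driven additions.** The same section says "Preliminary analyses will test for significant differences in demographic factors between the MATCH and waitlist groups; significant factors will be covaried in our models". Recruiting clinic is not a demographic factor, so this rule does not clearly reach it.
- **Clustering.** The growth-curve models are to "account for the nested structure of the data as well as potentially unequally spaced time points". The level of nesting is not named.

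**The concern.** The primary objective is to show that emotion regulation is a mechanism of change, so the quantity that matters most is the indirect effect: the product of the treatment-to-mediator path (a) and the mediator-to-symptom path (b). Randomisation protects a and the total effect. It does not protect b, because children are not randomised to a level of emotion-regulation change. Any common cause of mediator change and symptom change biases b unless it is adjusted for.

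Recruiting clinic is an obvious candidate for such a common cause. It is known for every child before randomisation, yet neither the design nor the model deals with it. If the two clinics differ in how much children change on both regulation and symptoms, part of that shared difference will be read as mediation. A larger sample does not remove this error.

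**Working it through.** **Inputs from the protocol (Sample Size).** The section states "moderate treatment effect ($d = 0.5$) α of 0.05 and β of 0.2", 25% mediated and a required N of 168. The target indirect effect is therefore 0.25 × 0.5 = 0.125. With 1:1 allocation (assumed, as the ratio is not stated), 168 gives 84 per arm.

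**Assumed, because the protocol does not give them.** Path values a = 0.5 and b = 0.25 (product 0.125); two-sided testing; the site split; the site effects on change.

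**Step 1: the plan's own figure.** A mediation simulation with 2,000 replications and these paths gives power of 0.80 to 0.82 at N = 168, so the stated size is reproduced. It depends on the assumed paths: over a = 0.3 to 0.7, with the product held at 0.125, power runs from about 0.49 to 0.82.

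**Step 2: chance imbalance and the treatment effect.** Let p be one site's share, d the site difference in change (in SD), and n = 84 per arm.
- SD of the between-arm difference in site share = √(2p(1−p)/n). With p = 0.30: √(0.42/84) = 0.0707, so the 95% range is ±1.96 × 0.0707 = ±0.139.
- 95% shift in the treatment estimate = 0.139 × d. For d = 0.2 this is 0.028 SD; for d = 0.5 it is 0.069 SD.
- Treatment standard error = √(2/84) = 0.154.
- Outcome variance due to site = p(1−p)d²/(1 + p(1−p)d²). For d = 0.2: 0.0084/1.0084 = 0.8%. For d = 0.5: 0.0525/1.0525 = 5.0%. Adjustment would shorten the standard error by about 0.4% and 2.5%.

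These shifts average to zero over randomisations. In 4,000 simulated trials per scenario (50:50 or 80:20 split, site effects 0.2 to 0.5 SD), the mean total effect was about 0.50 with or without site. Its standard error was 0.155 to 0.162 without site and 0.154 to 0.155 with it.

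**Step 3: the mediator-outcome path.** Let site shift mediator change by g and, holding the mediator fixed, shift symptom change by the same g in the same direction, with unit residual variance for the mediator. With site omitted, b tends to

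b* = b + g²p(1−p) / (1 + g²p(1−p)).

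Multiplying by a = 0.5 gives the indirect effect, set beside the simulated means:

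| Split | g | b* | Indirect effect, formula | Simulated, site omitted | Simulated, site included |
|---|---|---|---|---|---|
| 50:50 | 0.2 | 0.260 | 0.130 | 0.130 | 0.125 |
| 50:50 | 0.3 | 0.272 | 0.136 | 0.135 | 0.124 |
| 50:50 | 0.5 | 0.309 | 0.154 | 0.155 | 0.125 |
| 80:20 | 0.2 | 0.256 | 0.128 | 0.129 | 0.126 |
| 80:20 | 0.3 | 0.264 | 0.132 | 0.132 | 0.126 |
| 80:20 | 0.5 | 0.288 | 0.144 | 0.144 | 0.125 |

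Against the true 0.125, the simulated excess runs from 0.129/0.125 = 1.03 to 0.155/0.125 = 1.24, that is 3% to 24%. The apparent proportion mediated is 0.129/0.5 = 26% to 0.155/0.5 = 31%, instead of 25%.

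**Step 4: opposing site effects.** If site raises one variable and lowers the other, the added term changes sign. At 50:50 and g = 0.5, b* = 0.25 − 0.0625/1.0625 = 0.191 and the indirect effect is 0.096, about 24% too low.

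**The case against.** Several objections are fair, and they limit the point.

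- **A reader might infer that the omission biases the treatment effect.** It does not. Imbalance in an unstratified factor is chance variation that ordinary standard errors already include. Step 2 shows it is small.
- **A reader might infer that the clinics are known to differ in wait length, assessors or physiological recording.** The protocol does not say so, and in part it points the other way. Study Design describes the planned duration as close to usual waits at both clinics. Behavioural/Cognitive Tasks and Physiological Measures describe one recording system and one task set for all children. Data Collection puts questionnaires for both sites on a single platform for consistency. A contrast in referral routes is also an inference, since only CAMH's routes are described.
- **The models analyse change.** A stable site difference in symptom level largely drops out of latent change scores and slopes. Only a site difference in change matters, and 0.5 SD would equal the planned treatment effect, so the upper end of the range is demanding.
- **The nesting phrase could be meant to cover clinic.** It does not exclude this, but beside the remark on timing it reads most naturally as repeated measures within child. Two sites are too few to estimate a random effect, so a fixed term would be needed in any case.
- **Covariates can be left to a statistical analysis plan.** That is often so, but this protocol itself fixes a named list for both approaches, and the point concerns what that list contains.

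What stands is that a known, pre-randomisation grouping is handled nowhere, in an analysis whose key path randomisation does not protect.

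**Conclusion.** The point holds as a possible confounding of the mediator-outcome path, not as a bias in the treatment comparison. For the total effect and the a-path, the cost of omitting site is a little precision: a 95% chance shift of roughly 0.03 to 0.07 SD against a standard error of 0.154. For the indirect effect the error is systematic, about 3% to 24% upward under same-direction site effects of 0.2 to 0.5 SD on both variables, and downward if the effects oppose each other. If site affects change in only one of the two variables, or in neither, there is no such confounding. The size rests entirely on the assumed split, site effects and path values, so the percentages show what could happen and do not estimate what will. The change is nonetheless worth making, because it bears on the primary objective and costs almost nothing.

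**What to change.** In Data Analysis, add site (CAMH versus Guelph) to the covariate list as a fixed effect, entered regardless of any baseline significance test. In the pre-post model, regress both the change in emotion regulation to 3 months and the change in symptoms to the post assessment on site. In the trajectory model, regress the growth factors of both the weekly regulation measure and the weekly symptom measure on site. State in the same place which level the nesting refers to.

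The cost is one degree of freedom per equation. Recruiting clinic is known for every child, so no new data are needed. The randomisation scheme does not change and N = 168 is essentially unaffected. Adjustment removes confounding by site only; other common causes of mediator and symptom change remain an assumption of the mediation analysis.

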At the post-test assessment, families in to the usual care condition will complete the Service Access Form to report any external services (e.g. couples therapy, psychoeducational assessment) they accessed while on the waitlist for usual care, or participating in usual care. It is common for families to be waiting for treatment from multiple services, or to seek private therapy while they are on our clinic's waitlist. This which will allow us to evaluate any pre-post change that may be due to those services. Families in the intervention condition will report on their access and use of external services at their 1-year follow up assessment.

Physiological Measures

Heart rate variability (HRV) and skin conductance level (SCL) will be measured using the widely used, non-invasive, compact mobile testing unit from *BIPAC*. This unit consists of two transmitter modules and a transducer (attached to two nylon belts and electrodes) that transmits physiological data to the BioNomadix Logger (BN-Logger), which is a battery-operated, wearable physiological recording platform capable of digitally storing signals for long periods of time. The comfortable system will be worn by the child as a bracelet and two belts for duration of the Trier Social Stress Test, the Pinata Task, Cognitive Reappraisal Task and Parent-Child Interaction.

MATCH Treatment

The intervention arm of this project will consist of a transdiagnostic psychotherapy treatment: *The Modular Approach to Therapy for Children with Anxiety, Depression, Trauma, or Conduct Problems (MATCH-ADTC)*⁴².

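### The pre-post FIML model, as described, ignores the weekly symptom course and the 3-month CBCL/YSR, so it does not protect the MATCH contrast if course-related dropout differs by arm

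*Protocol*

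**What the plan says.** The Data Analysis section of the protocol sets out two mediation analyses. In the first (pre-post), MATCH versus waitlist is the predictor. Emotion regulation is the mediator and "will be modeled as a latent change from baseline to the 3-month quarterly assessment". For the outcome, "symptom change (CBCL/YSR internalizing and externalizing scores) will be modeled as a latent change from baseline to the post assessment". In the second (trajectory), slopes of weekly CADS and weekly BFS are related to each other. Both models adjust for age, sex or gender, medication, puberty, ethnicity and fidelity. On missing data the section says: "We will apply an intent-to-treat approach and full information maximum likelihood estimation to account for potential bias caused by missing data". Auxiliary variables are neither named nor ruled out.

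Other sections bear on this:
- **Study Design and the measurement table:** weekly BFS and CADS are collected in both arms, and CBCL and YSR are repeated at the quarterly visit.
- **Consent and Assent:** once a family withdraws, no further visits or measures follow.
- **Sample Size:** attrition is expected in "the intervention arm and the waitlist arm to be 20%, so we increased our sample size to 202".
- **Covariates:** it is common for families to wait for several services "or to seek private therapy while they are on our" clinic's waitlist.

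**The concern.** Full information maximum likelihood is only as good as the information in the model. If a family's decision to leave depends on how the child has been doing in recent weeks, and the likelihood contains no measure of those weeks, dropout is not ignorable given what is modelled. The weekly scores are the most direct record of that course. For families who leave after the quarterly visit, the 3-month CBCL/YSR is the closest earlier reading of the outcome itself. As described, the first model uses neither.

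The circumstances of staying also differ by arm. A family that withdraws after starting MATCH keeps its treatment (Consent and Assent). A waitlist family keeps its place in the queue, must complete 75% of weekly measures, and is offered bridging treatment after the post-assessment (Control Group). Dropout that works differently by arm is therefore plausible. What is at stake is chiefly the MATCH contrast on CBCL/YSR change, and through it the proportion mediated.

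**Working it through.** **The plan's own figures.** Inputs from Sample Size: d = 0.5, α = 0.05 (two-sided assumed), power 0.80, 25% mediated. The indirect effect is 0.25 × 0.5 = 0.125. The protocol does not state how this splits into paths; a = 0.5 and b = 0.25 give 0.5 × 0.25 = 0.125. Simulating a single-mediator model with 84 per arm gives joint-test power of 0.79 to 0.80, so N = 168 reproduces. Other splits tried give 0.48 to 0.73. The 202 is 168 × 1.2 = 201.6. Dividing by 1 − 0.2 would give 210, which is a separate matter. At 20% attrition, 202 × 0.8 = 161.6 complete.

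**The missing-data check.** The protocol gives no dropout mechanism, so one must be assumed. The set-up was a linear symptom course, monthly readings of the weekly scale, monotone dropout, and a true contrast of 0.50 SD. The log-odds of dropout range from 0.5 to 2 in size per unit of weekly change; a positive value means leaving is likelier as symptoms rise. FIML was computed as the factored likelihood of a saturated normal model. It contained arm, baseline symptoms, baseline and 3-month mediator, and post score, first without and then with the weekly readings (n = 600,000). Bias = 0.50 minus the estimate without weekly scores.

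| Log-odds, waitlist / MATCH | Dropout, waitlist / MATCH | Without weekly | With weekly | Bias |
|---|---|---|---|---|
| 0 / 0 | 20% / 20% | 0.50 | 0.50 | 0.00 |
| 1 / 1 | 20% / 20% | 0.49 | 0.50 | 0.01 |
| 2 / 2 | 20% / 20% | 0.49 | 0.50 | 0.01 |
| 0.5 / 0 | 20% / 20% | 0.46 | 0.50 | 0.04 |
| 1 / 0 | 20% / 20% | 0.43 | 0.50 | 0.07 |
| 2 / 0 | 20% / 20% | 0.38 | 0.50 | 0.12 |
| 0.5 / −0.5 | 20% / 20% | 0.43 | 0.50 | 0.07 |
| 1 / −1 | 20% / 20% | 0.36 | 0.50 | 0.14 |
| 2 / −2 | 20% / 20% | 0.26 | 0.50 | 0.24 |
| −1 / 1 | 20% / 20% | 0.63 | 0.50 | −0.13 |
| 1 / 1 | 30% / 10% | 0.42 | 0.50 | 0.08 |
| 1 / 1 | 10% / 30% | 0.57 | 0.50 | −0.07 |

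If one dropout rule applies to both arms and the rates differ only because the arms' symptoms diverge (20% against 17% at log-odds 1, 20% against 14% at log-odds 2), the estimates are 0.48 and 0.46, a bias of 0.02 and 0.04.

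**Sensitivity.** The result depends on how much of the course the 3-month mediator already carries. At log-odds of 1 per SD of weekly score and 20% dropout per arm, other assumed correlations give:
- **Waitlist-only dependence:** 0.42 to 0.47 without weekly scores.
- **Opposite directions:** 0.34 to 0.42 without weekly scores.

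The upper ends belong to a mediator correlated 0.5 to 0.6 with the weekly and post scores.

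**Scale and precision.** In samples of 202 the SD of the estimate is about 0.15 to 0.16 (0.14 to 0.16 allowing for other assumptions). A bias of 0.04 is about a quarter of that (0.04/0.16 = 0.25), and 0.24 is 1.6 times it (0.24/0.15). With random dropout the SD falls from 0.160 to 0.155, a factor of 0.97; across assumptions the gain is 2 to 4%.

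**The mediator path.** The effect of arm on the 3-month mediator, about 0.50 in truth, stayed between 0.46 and 0.52 throughout. The distortion falls mainly on the symptom contrast. Bias in the product of paths was not computed.

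**The case against.** The strongest objection is that the choice of auxiliary variables usually belongs in a statistical analysis plan. The protocol is silent on them, and a plan not shown here may add them. That limits the point: a reader might infer that the protocol excludes the weekly data from the missing-data handling, and it does not. But the protocol itself fixes the variables of the pre-post model and itself relies on FIML for missing-data bias. Better information is already being collected, so naming it improves the stated method and does more than supply a missing detail.

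Second, the bias is conditional. A reader might infer that course-related dropout biases the contrast as such. The figures do not support this: with equal dependence and equal rates the bias is about 0.01, and the protocol expects 20% in each arm.

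Third, the mechanism is assumed. A reader might infer that worsening waitlist families leave for private therapy and that improved MATCH children stop. The Covariates section describes families who report outside services at the post-test, hence families who stayed. No section says that improved MATCH children leave the study. Treatment length is flexible and the post visit follows completion, so early improvement can mean an earlier post score. This stands, and it leaves the size and sign open.

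Fourth, the trajectory model already uses the weekly scores under FIML. True, but it addresses a different question and does not protect the CBCL/YSR contrast.

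Fifth, full recovery of 0.50 is partly built in, because simulated dropout depended on the observed weekly scores. This also stands.

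Finally, a reader might infer that children with a missing covariate would be dropped. That rests on a software default, and the protocol names no software.

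**Conclusion.** The point holds conditionally. As described, the pre-post FIML conditions on arm, baseline, the 3-month regulation change and the listed covariates, but not on the weekly course or the 3-month CBCL/YSR. It therefore secures its stated purpose only if dropout is unrelated to that course given those variables, or related in the same way and at the same rate in both arms. Where dependence or rates are assumed to differ by arm, the MATCH contrast is off by about 0.04 to 0.24 SD, in either direction, on a true 0.50; the mildest case, a common rule with slightly unequal rates, gives 0.02. Where they do not differ, there is no material bias and a precision gain of 2 to 4%. All these sizes rest on assumed dropout mechanisms and correlations, since the protocol supplies neither. They show what could happen and do not predict this trial's bias. The change is worth making because it is cheap, not because bias has been shown.

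**What to change.** In the Data Analysis section, after the FIML sentence, state that the pre-post models will include auxiliary variables: the 3-month CBCL in the CBCL model, the 3-month YSR in the YSR model, and a small set of weekly summaries. Parent BFS and parent CADS would serve, either at the last observed week or averaged over a fixed early window. The fixed window means the same thing for completers and dropouts; the last observed week lies closer to the decision to leave. Choose one in advance. The auxiliaries should correlate with the model variables or their residuals without becoming predictors, so that the analysis model and its estimand are unchanged.

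Keep the set small. With 202/2 = 101 per arm, last value and slope for both scales and both reporters would make 2 × 2 × 2 = 8 auxiliaries, too many to carry with arm-specific associations. A slope up to dropout is undefined for completers. Child CADS is collected only from age 9, while entry is from age 8.

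The cost is slightly more model code and a somewhat larger model; no new data are needed. The check above used all monthly readings of a weekly symptom scale. The reduced set and the 3-month CBCL/YSR were not simulated, and correction will be complete only to the extent that dropout depends on the scores included.
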